--	--

Adverse Event Screening At each medication visit participants will be queried regarding the presence of any new symptoms or concerns. We will specifically query the adverse effects that occurred at a frequency that exceeded placebo in either the 3 month pivotal trials²² or the 1-year study²³ including somnolence, fatigue, dry mouth, dyspepsia, and peripheral edema. We will also specifically query the pre-specified events of interest for those trials including suicidal ideation, complex sleep-related behaviors (e.g. getting food during the night and not remembering it), sleep onset or off-set hallucinations, sleep paralysis, and falls. Excessive daytime sleepiness will be assessed by administering the Epworth Sleepiness Questionnaire.³¹ Weight and vital signs will be obtained at each study visit. At the post-treatment visit specific inquiry will also include the occurrence of common medication withdrawal symptoms such as dizziness, shaking, nausea, and muscle tension as well as re-assessment of insomnia and sleep patterns for that period.

Polysomnography (PSG):

PSG collection includes a standard electroencephalogram (EEG) montage with two central, frontal, and occipital leads, two electrooculograms, chin and limb electromyograms, and an electrocardiogram (ECG). Recordings will be conducted using an Embla (Denver, CO) Titanium unit in the CRU. Screening for sleep disordered breathing and limb movements will be performed using the screening night data. Visual scoring of sleep records from a computer monitor will be done following the American Academy of Sleep Medicine (AASM) Manual, Version 2.0.³² The REMLogic software (Embla) will calculate sleep parameters including TST, SOL, WASO, the percentage of each sleep stage, and mean duration of continuous REM segment. Calculation of REM segment length used our previous criteria¹⁶ of at least two epochs of consecutive REM sleep with no more than one 30-sec epoch of non-REM sleep interruption. The sleep parameters for baseline will be obtained from the second night recording after an accommodation recording that will also screen for apnea will be used in data analysis. Respiratory strain gauge, nasal air flow, and oximetry monitors will be included on the first but not subsequent nights. Participants will be instructed to go to bed near their habitual bedtimes and will wake up naturally. PSG will be done prior to medication and after 3 weeks of medication treatment to allow for stable dosing.

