2.7 Statistical Analysis and Sample Size Justification	
The data will be analyzed by the Investigator and Co-investigator.
 
Main outcomes will be ISI, CAPS nightmare frequency and total score, diary and PSG sleep latency and WASO at week 3 and for non-PSG variables Med week 6. We will also explore effects on REM and SWS and their relationships to other study outcomes.
 
An alpha level of .05 (one-tailed) will be applied in testing Hypotheses 2a), 2b), 2d), and 2e). Initially, data will be pre-screened for errors, outliers, normality of distributions, and any necessary modifications, such as transformation of variables and/or elimination of cases, will be conducted.
 
Our initial objectives are descriptive. We will generate frequencies of types of trauma exposures associated with insomnia and the rates for PTSD diagnoses and sub-diagnostic threshold PTSD symptoms in the recruited study population (Objective 1) and the frequency of adverse events (Objective 2). The latter will be descriptively contrasted to the extant data for suvorexant from the insomnia registry trials as a guide to planning future trials including dosing.
 
Hypothesis 2a) Insomnia will improve, and nightmares and other PTSD symptoms will be reduced with suvorexant treatment compared with placebo: We will compare baseline characteristics of the treatment groups using independent samples t-tests for continuous variables or chi-square tests for categorical variables. If a significant group difference is found in some of the variables, the variable(s) will be included in subsequent analyses as a covariate(s). We will perform 2 (Group) x 3 (Time: baseline, Med week 3, and week 6) mixed ANOVAs or ANCOVAs [if there is a covariate(s)] to compare the changes in ISI scores, nightmare frequency, and CAPS scores, separately, between the two groups.
 
Hypothesis 2b) Improved sleep will be associated with reduced non-sleep PTSD symptoms: Correlation coefficients between baseline – Med week 6 changes in sleep measures (e.g., ISI scores and nightmare frequency) and changes in the CAPS scores excluding two sleep-related items will be computed. In addition, we will exploratively examine if there is an interaction with treatment condition by performing regression analyses in which CAPS scores will be predicted by changes in sleep measures, treatment condition, and a Sleep measure X Treatment condition interaction.
 
Hypothesis 2d) Sleep latency and wake after sleep onset (WASO) will be reduced with suvorexant treatment compared with placebo: We will perform 2 (Group: suvorexant vs. placebo) x 2 (Time: Baseline and Med week 3) mixed ANOVAs or ANCOVAs [if there is a covariate(s)] to compare the changes in PSG measured sleep latency and WASO between the suvorexant and placebo groups.
 
Exploratory hypothesis 2e) When reduced at baseline (i.e., SWS below 100 minutes and mean REM segment duration below 15

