
	
minutes), SWS and the duration of continuous segments of REM sleep will increase with suvorexant than placebo: Participants with reduced baseline SWS (below vs. above 100 minutes) and mean REM segment duration (below vs. above 15 minutes) will be included in the analyses. 2 (Group) x 2 (Time: Baseline and Med week 3) mixed ANOVAs or ANCOVAs will be performed to compare treatment changes in SWS and REM segment duration between the suvorexant and placebo groups.
 
Power Considerations:
 
G*Power 3.1 ³³ was used to conduct power analysis.
 
Power analysis for Hypothesis 2a) is based on the effect size estimated using findings of Herring and colleagues' ²² placebo controlled trial of suvorexant in adults with insomnia. Since there are no data for suvorexant on trauma related nightmares and PTSD symptoms, we also used Taylor and colleagues' ²⁴ placebo controlled trial of prazosin in civilian outpatients with PTSD, sleep disturbances, and nightmares. Taylor et al. found a large-size effect of prazosin on changes in trauma-related nightmare severity compared with placebo ($d = 0.96$ or $f = 0.48$) and PTSD severity ($d = 0.79$ or $f = 0.40$) and a medium-size effect on changes in trauma-related insomnia symptoms severity ($d = 0.50$ or $f = .25$). Herring and colleagues found a small-size effect of a 1-month suvorexant treatment (20mg for nonelderly and 15mg for elderly) on insomnia severity measured by the ISI ($d = 0.39$ or $f = 0.20$). To detect an $f = 0.20$ Group x Time interaction effect in the proposed mixed ANOVA with 80% power, a total of 42 participants are needed.
 
Power analysis for Hypothesis 2b) is based on the effect sizes estimated using Krakow and colleagues' findings ³⁴ from their study examining effects of cognitive behavioral therapy for nightmares and insomnia in crime victims with PTSD. They found correlations between changes in nightmare frequency, insomnia severity, and sleep quality and changes in overall PTSD symptom severity ranging from $r = .37$ to $.40$. A sample size of 43 will allow for detecting similar size effects with 80% power.
 
Power analysis for Hypothesis 2d) is based on findings from the aforementioned Herring and colleagues' study. They found that effects of suvorexant on sleep latency and WASO were $f = 0.17$ and 0.31, respectively. To detect an effect size of 0.17 using the proposed mixed ANOVA with 80% power, a total of 70 participants are needed.
 
Power analysis for Exploratory hypothesis 2e) is based on findings from the aforementioned Taylor and colleagues' study. They found that the effect of prazosin on mean REM period duration was $f = 0.50$. Using the proposed mixed ANOVA, a total of 16 participants will allow for detecting a large size within-between interaction effect ($f = 0.50$) with 80% power.

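### Hypothesis 2d tests raw change from one baseline PSG night; adjusting week 3 for the baseline PSG values already recorded would gain precision at little cost

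*Combined protocol and SAP*

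**What the plan says.** The flowchart in section 2.4 marks two PSG recordings at baseline and one at Med week 3. Section 2.5 (Polysomnography) explains the two baseline nights: "The sleep parameters for baseline will be obtained from the second night recording after an accommodation recording that will also screen for apnea". Respiratory strain gauge, nasal airflow and oximetry are worn on the first night only. On timing it says "PSG will be done prior to medication and after 3 weeks of medication treatment to allow for stable dosing", and describes no accommodation night before the week 3 recording.

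Section 2.7 lists PSG sleep latency and WASO at week 3 among the main outcomes. Hypothesis 2d is tested by "2 (Group: suvorexant vs. placebo) x 2 (Time: Baseline and Med week 3) mixed ANOVAs or ANCOVAs" in order "to compare the changes in PSG measured sleep latency and WASO between the suvorexant and placebo groups". The covariate rule is given under Hypothesis 2a: a variable becomes a covariate only if the arms differ significantly on it at baseline.

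The 2d power paragraph drives the sample size: "To detect an effect size of 0.17 using the proposed mixed ANOVA with 80% power, a total of 70 participants are needed". Section 2.5 expects to recruit 90 and retain 70.

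**The concern.** With two time points, the Group x Time test in a mixed ANOVA is the same as a two-sample test on week 3 minus baseline. That test gives the baseline value a fixed coefficient of 1. When two single nights in the same person correlate only moderately, the fixed coefficient carries the noise of the baseline night into the outcome. ANCOVA estimates the coefficient and removes that part of the noise.

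The plan would use ANCOVA only if a baseline test happened to be significant. The gain from adjustment comes from how well baseline predicts week 3, not from imbalance, so this trigger does not serve precision. A further pre-treatment night is recorded for every participant and contributes nothing to 2d.

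At stake is the power of the comparison that sets the trial's size. The 70 participants needed for 2d equal the number expected to be retained, so there is no margin beyond that.

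**Working it through.** **Inputs from the documents.** 2d effect sizes: "They found that effects of suvorexant on sleep latency and WASO were $f = 0.17$ and 0.31, respectively". Power 80%, N = 70, G*Power 3.1, two time points.

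**Assumptions.** Equal allocation, equal SD at baseline and week 3, and a correlation r between single nights of 0.3 to 0.6. The documents give none of these.

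**1. The plan's own figure.** For the within-between interaction, lambda = f^2 x N x m / (1 - rho), with 1 and N - 2 degrees of freedom. With f = 0.17, N = 70, m = 2 and rho = 0.5, lambda = 0.0289 x 70 x 2 / 0.5 = 8.09. At 0.05 on the F test the power is 0.801, so N = 70 reproduces. The result depends on the unstated rho: 0.3 gives N = 98 and 0.7 gives N = 44. I take f at face value. The F test is non-directional although the plan declares one-tailed testing (one-tailed N would be 56); that is a separate matter.

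**2. Variance of the outcome under three analyses** (single-night SD = 1, all pairs of nights correlated r):
- planned change score: 2 - 2r
- ANCOVA on night 2: 1 - r^2
- ANCOVA on nights 1 and 2 as separate covariates: 1 - 2r^2/(1 + r)

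| r | change | night 2 | both nights | change / night 2 | change / both | night 2 / both |
|---|---|---|---|---|---|---|
| 0.3 | 1.40 | 0.91 | 0.862 | 1.54 | 1.625 | 1.056 |
| 0.4 | 1.20 | 0.84 | 0.771 | 1.43 | 1.56 | 1.089 |
| 0.5 | 1.00 | 0.75 | 0.667 | 1.33 | 1.50 | 1.125 |
| 0.6 | 0.80 | 0.64 | 0.550 | 1.25 | 1.45 | 1.164 |

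Most of the gain comes from adjusting for night 2 at all.

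**3. In terms of power.** At r = 0.5, the value that reproduces the plan, dividing the variance by 1.33 takes the required N from 70 to 54, or power at 70 from 0.80 to 0.90. With both nights, N is 48 and power 0.93. These figures are before the degree-of-freedom cost in step 5. At r = 0.3 the planned test has lambda = 0.0289 x 70 x 2 / 0.7 = 5.78 and power 0.66. ANCOVA on night 2 has lambda = 5.78 x 1.54 = 8.9 and power 0.84. Adjustment helps most where the planned test is weakest.

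**4. If night 1 predicts week 3 less well than night 2 does.** Set r(1,2) = r(2,week 3) = 0.5 and let x = r(1,week 3). Then R^2 = (0.25 + x^2 - 0.5x)/0.75, against 0.25 for night 2 alone.
- x = 0.5: R^2 = 0.333, ratio 0.75/0.667 = 1.125
- x = 0.4: R^2 = 0.280, ratio 0.75/0.720 = 1.042
- x = 0.3: R^2 = 0.253, ratio 0.75/0.747 = 1.004
- x = 0.25: R^2 = 0.250, ratio 1.000

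**5. Cost of the extra covariate.** With q covariates, chance imbalance inflates the variance of the treatment effect by about 1 + q/(N - q - 3). At N = 70 this is 67/66 for one covariate and 67/65 for two, so the second costs 66/65 = 1.015. The net effect of adding night 1 in step 4 is then 1.125/1.015 = 1.108, 1.042/1.015 = 1.026, 1.004/1.015 = 0.989 and 1/1.015 = 0.985. That runs from an 11% gain to a loss of 1 to 2%.

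**6. Bias.** A shift at week 3 shared by both arms drops out of the arm contrast. In a simulation with a common shift of 0.5 SD and a true difference of -0.34, the mean estimate was -0.337.

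**The case against.** Taking baseline from the night after an accommodation night is a stated and sensible choice. Night 1 is not wasted, since it serves the apnea and limb-movement exclusion. Both points stand, and nothing here makes night 2 the wrong baseline to describe.

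A reader might infer that night 1 is the proper match for week 3, because neither has a laboratory night just before it. The documents do not support that. Night 1 is the first night in the unit and carries respiratory sensors that later nights lack. Night 2 and week 3 share the recording set-up, and by week 3 participants have already slept there twice. How unadapted they are at week 3 is unknown.

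A reader might also infer that the mismatch biases 2d. It does not, unless the re-adaptation effect differs by arm.

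The second night's gain of 6 to 16% needs three exchangeable nights. If night 1 is a poorer predictor, the gain falls to nothing, so it is neither assured nor free. It is still not a serious risk. Larger losses arise if the two nights are averaged, which forces equal weights: in the change-score analysis the required N could go from 70 to as low as 54 or as high as 86, depending on how noisy night 1 is. Separate covariates let the data set the weights, and the downside is then about 1 to 2%.

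**Conclusion.** The point holds as a matter of precision. The planned change-score test for 2d has 1.54 to 1.25 times the variance of an ANCOVA on night 2, for r from 0.3 to 0.6. The one degree of freedom for night 2 costs about 1.5% of that. Night 1 as a further covariate adds between about 0 and 16% before its own 1.5% cost. All of this rests on assumed correlations and equal SDs, so the sizes are indicative. The night 2 gain is a factor of 2/(1 + r), which exceeds 1 for any r below 1.

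The documents do not show a biased comparison, a wrong baseline night or a guaranteed gain from night 1.

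One caution on interpretation remains. Baseline follows an accommodation night, and none is described before week 3. Any re-adaptation effect would therefore be mixed into the change within each arm, and only the between-arm contrast is interpretable as a treatment effect.

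**What to change.** In section 2.7, replace the 2 x 2 mixed ANOVA for 2d with an ANCOVA of week 3 PSG sleep latency, and likewise WASO, on treatment and the night 2 value. Include the night 2 value whether or not the arms differ significantly at baseline.

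Add the night 1 value as a second, separate covariate, not averaged with night 2. Specify the model with night 2 alone as the sensitivity analysis. State how a missing or failed night 1 recording is handled, and apply any transformation identically to all three nights. Keep night 2 as the baseline in descriptive tables, and state that within-arm PSG change will not be read as improvement.

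The cost is SAP wording and one degree of freedom for each baseline night. There are no new visits or recordings. Night 1 needs full stage scoring if the apnea and limb-movement screen does not already provide it, which is at most about 90 records. If that is not affordable, the night 2 adjustment alone keeps most of the benefit and needs no extra scoring.

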
2.1 Objectives & Hypotheses
	
Disturbed sleep is one of the most common and distressing responses to exposure to severe trauma and can persist in many of those affected with and without accompanying posttraumatic stress disorder (PTSD). Insomnia is a risk factor for many of the conditions that are prevalent in trauma-exposed populations including PTSD, depression, and physical health conditions such as obesity, and cardiovascular disease. Trauma-related insomnia (TRI) is not typically differentiated in studies characterizing insomnia and its treatment, and insomnia accompanying PTSD has been shown to be relatively refractory to the treatments that are established for PTSD. Thus treatment of TRI presents an unmet need that has implications for the large and growing groups of people exposed to trauma in terms of relieving distress and preventing further psychiatric and medical morbidity.
 
Most of the data on TRI comes from research on populations with PTSD. Difficulty initiating and maintaining sleep is designated as one of the heightened arousal symptoms of PTSD in the DSM. Sleep studies have suggested reduced slow wave sleep (SWS) in some PTSD populations and fragmented rapid eye movement (REM) sleep when PTSD is developing, and during its more acute stages. Suvorexant is a first in class orexin antagonist and is approved by the FDA for the indication of insomnia. Orexin antagonists dampen the activity of a specific arousal enhancing system in the brain during sleep. In rodent models suvorexant has been shown to enhance, and in healthy humans, to not affect slow wave and REM activity (in contrast with traditional hypnotics which can diminish both). Reducing arousal during sleep while maintaining REM and slow wave sleep is a promising profile for the treatment of TRI. We are therefore proposing a placebo controlled evaluation to assess the efficacy of suvorexant for treating TRI with and without PTSD and its tolerability in these populations. We will include polysomnography (PSG) in order to probe potential mechanisms and biomarkers predicting response. The proposed study will meet the objectives below and test the following hypotheses:
 
Objective 1. To recruit a group of participants that meet criteria for insomnia and who identify a severely threatening event (DSM criterion A trauma) as a precipitant or a factor that significantly exacerbated their sleep disturbance; and to determine the frequency of PTSD diagnoses and symptoms among the recruited participants.
 
Hypothesis 1) – Recruitment will reveal TRI to be a common condition that in approximately half of cases occurs absent PTSD.
 
Objective 2. To evaluate the effectiveness and tolerability of suvorexant on insomnia and when present, associated PTSD symptoms and its effects on PSG measures in participants with TRI.
 
Hypothesis 2a) Insomnia will improve, and nightmares and other PTSD symptoms will be reduced with suvorexant treatment compared with placebo.
 
2b) Improved sleep will be associated with reduced non-sleep related PTSD symptoms when present.

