The following diagnostic and outcome assessments will be performed by research staff members blind to participants' treatment condition.

	
(Diagnostic)
 
Duke Structured Interview Schedule for DSM-IV-TR and International Classification of Sleep Disorders 2nd edition (ICSD-2) Sleep Disorder Diagnoses (DSISSD)²⁶ – A widely used semi-structured interview designed to assess sleep disorder diagnostic status. We will use this interview to evaluate the presence of insomnia and to rule out insomnia that is accounted for by a mental disorder other than PTSD, medical conditions, and substance use, parasomnias, narcolepsy, and circadian rhythm sleep disorders. This interview will establish the onset and course of insomnia, with in conjunction with the information from the LEC and CAPS (see below) will determine the criteria for “trauma-related.”
 
Structured Clinical Interview for DSM-V (SCID)²⁷ The SCID is semi-structured diagnostic interview that assesses the DSM diagnostic criteria for psychiatric disorders and is considered the “gold standard” for assessing mental disorders. A modification will be utilized in order to screen for excluded and establish allowable comorbid conditions.
 
Life Event Checklist (LEC),²⁸ is an inventory of lifetime exposure to traumatic events that lists 15 of the more common categories of trauma experiences and asks for endorsement of whether they occurred directly to the person or were witnessed and the age of exposure.
 
The Clinician Administered PTSD Scale (CAPS)²⁹ will be administered to further assess the details of trauma exposure, and (past week) PTSD severity, and lifetime diagnostic criteria. The CAPS evaluates the frequency and intensity of each of the 17 symptoms of PTSD and is considered a gold standard for assessment of the diagnosis and severity of PTSD.
 
(Assessments used for outcomes)
 
Insomnia Severity Index (ISI)³⁰ The ISI is a seven-item measure used to evaluate insomnia severity for the past two weeks. Items are scored on a 5-point scale and a total score is obtained by summing the seven items, with higher scores indicating greater insomnia severity. A cutoff score of 10 has been determined to be optimal for detecting insomnia in population samples. The ISI is also validated as an outcome measure for insomnia treatment studies and is widely used for that purpose.
 
Sleep diary - Participants will complete our standard sleep diary each morning throughout this trial. The diary includes questions about bedtime, final awakening time, sleep onset latency (SOL) estimate, the number of awakenings, and duration of each awakening, overall sleep satisfaction, morning restfulness, adherence/non-adherence to the study medication regimen, nightmare frequency, and content of nightmare. Estimated total sleep time (TST) and wake after sleep onset (WASO) for each night will be calculated using information provided in the diary.
 
One week CAPS nightmare item and total score minus sleep items.

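### The CAPS outcome for Hypothesis 2a has two definitions, and the one in section 2.7 would test non-sleep PTSD symptoms on a score that includes the sleep items

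*Combined protocol and SAP*

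**What the plan says.** Hypothesis 2a (section 2.1, repeated in 2.7) predicts that insomnia will improve and that "nightmares and other PTSD symptoms will be reduced with suvorexant treatment compared with placebo". It therefore has three targets: insomnia, nightmares, and the rest of the PTSD picture.

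The CAPS variable attached to the third target changes from place to place:

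- Section 2.5, in the list of assessments used for outcomes, gives the one-week CAPS "nightmare item and total score minus sleep items".
- Section 2.7, main outcomes: "Main outcomes will be ISI, CAPS nightmare frequency and total score". Nothing is excluded.
- Section 2.7, the 2a analysis: mixed ANOVAs or ANCOVAs "to compare the changes in ISI scores, nightmare frequency, and CAPS scores, separately, between the two groups". Nothing is excluded.
- Section 2.7, the 2b correlations: "changes in the CAPS scores excluding two sleep-related items will be computed".
- Section 2.7, the 2b regression: "regression analyses in which CAPS scores will be predicted by changes in sleep measures". The exclusion has gone again, although 2b concerns non-sleep symptoms.

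Section 2.5 also says "The CAPS evaluates the frequency and intensity of each of the 17 symptoms of PTSD", so an unqualified total covers all 17. Neither section lists which items count as sleep items; section 2.7 says only that there are two.

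**The concern.** The score in section 2.5 and the score in the main-outcomes sentence of section 2.7 are different variables, and no text says which one tests the third part of Hypothesis 2a. Under section 2.7 as written, that part is tested on a score containing the nightmare item, already an outcome of its own, and the sleep-difficulty item. Section 2.1 itself points out the overlap: "Difficulty initiating and maintaining sleep is designated as one of the heightened arousal symptoms of PTSD in the DSM".

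The study drug is a hypnotic, the sample is selected for insomnia, and section 2.5 expects about half of participants not to meet criteria for PTSD. In that setting, movement in the two sleep items alone pushes the full total in the drug's favour and can be read as an effect on PTSD. Because both scores fit the plan, the choice could also be made after the results of each are known. Section 2.7 says the investigators will analyse the data themselves, so the text should fix the choice.

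**Working it through.** **The plan's own figure.** The only sample size for Hypothesis 2a is 42, from f = 0.20 on the ISI with 80% power (section 2.7, Power Considerations). For the Group x Time term with m = 3 time points, take λ = f²·N·m/(1 − r), with df = 2 and 2(N − 2). Assuming a correlation r = 0.5 between repeated measures and sphericity (neither is stated), λ = 0.04 × 42 × 3 / 0.5 = 10.08 with df 2 and 80. Power at the 0.05 level is 0.803, and 42 is the smallest even N reaching 80%. The figure reproduces. It rests on the ISI, so the definition of the CAPS score does not affect it.

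**Reading the passages together.** The bare term for the CAPS score appears twice in analysis sentences of 2.7. In the 2b regression it must mean the reduced score if it is to address 2b. In the 2a test it follows a main-outcomes sentence that names the total. The term therefore has no fixed meaning within 2.7, and only section 2.5 gives an explicit definition that covers 2a.

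**How much the full total could mislead.** The documents give no item SDs, inter-item correlations or item-level effects, so this is an illustration under assumptions.

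Inputs from the documents:
- 17 items (2.5), of which two are sleep-related (2.7)
- 70 retained participants (2.5), taken as 35 per arm
- one-tailed alpha of 0.05 (2.7)
- effect sizes from Power Considerations: 0.39 for suvorexant on the ISI; 0.96 and 0.50 for prazosin on nightmares and insomnia

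Assumed:
- items of equal variance
- a common inter-item correlation ρ of 0.1 to 0.5
- the cited scale-level effects applied to single CAPS items
- no effect on the other 15 items

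A sum of 17 unit-variance items has variance 17(1 + 16ρ), so the standardised effect on the total is

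d_total = (d₁ + d₂) / √[17(1 + 16ρ)].

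The denominator is √44.2 = 6.648 at ρ = 0.1 and √153 = 12.369 at ρ = 0.5. The numerator is 0.39 + 0.39 = 0.78 with the suvorexant effect on both items, and 0.96 + 0.50 = 1.46 with the prazosin effects.

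| d₁ + d₂ | ρ | d_total | One-sided t-test, 0.05 | Mixed ANOVA, Group x Time F at 0.05 |
|---|---|---|---|---|
| 0.78 | 0.1 | 0.117 | 12.3% | 7.2% |
| 0.78 | 0.5 | 0.063 | 8.3% | 5.8% |
| 1.46 | 0.1 | 0.220 | 23.1% | 14.0% |
| 1.46 | 0.5 | 0.118 | 12.4% | 7.2% |

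The last two columns give the percentage of trials in which the full total is significant although nothing but the two sleep items has moved. With the sleep items removed, the rate is 5% (4.9% in the simulated ANOVA). The t-test stands in for the one-tailed level in section 2.7. The ANOVA column simulates the planned 2 x 3 design: 20,000 runs, equal effect at weeks 3 and 6, compound symmetry, d in SDs of change.

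**The case against.** The best counter-argument is that section 2.7 is only abbreviating. Section 2.5 is where outcomes are defined, the main-outcomes sentence repeats the same pair in the same order, and the 2b regression shows that the authors shorten the term elsewhere. This reading is plausible. It does not settle the matter, because the exclusion is written out in full for the 2b correlations, so its absence from the 2a sentences can equally be read as deliberate.

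A second argument is that a full total in 2a and a reduced score in 2b would be coherent. In 2b the exclusion prevents sleep being correlated with itself, while 2a is a between-group comparison without that circularity. The power section also cites PTSD severity from the prazosin trial (d = 0.79) without mentioning any exclusion. The full total is indeed a legitimate measure of overall severity, and a treatment effect on it would be real. But it would not answer the third part of 2a, which sets nightmares apart from the remaining symptoms, and it would contradict section 2.5.

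Several smaller points stand. The two items can be inferred from the text even though they are not listed as such. The nightmare item would be one of 17 and the outcomes are tested separately, so the overlap is partial. The higher rejection rates come from the t-test stand-in or from another drug's effects; with the suvorexant effect and the planned type of test, the rate is only about 6% to 7%. Zero effect on the other 15 items is a scenario for measuring misattribution and not a forecast.

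**Conclusion.** The point holds. A named main outcome has two incompatible definitions in the current text, and section 2.7, followed literally, tests the non-sleep part of Hypothesis 2a on a score that includes the sleep items. This conclusion rests on the wording alone.

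The numerical consequence is modest and depends on the assumptions above. With the suvorexant effect on both sleep items, the false-attribution rate is about 6% to 7% for the mixed ANOVA and 8% to 12% for the one-sided t-test. With the prazosin effects it is about 7% to 14% and 12% to 23%. The comparison value is 5% throughout. Unequal item variances could move these figures in either direction. The plan should be corrected, but the defect does not undermine the trial.

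**What to change.** In section 2.7, use one term for the CAPS outcome in three sentences: the main-outcomes sentence, the 2a ANOVA sentence and the 2b regression sentence. The term should be the CAPS total without the two sleep-related items, with those items named (presumably nightmares and disturbed sleep; the investigators should confirm). This is the score that section 2.5 and the 2b correlations already specify. Keep the nightmare item as its own outcome. The full total can be reported as a labelled supportive result, but not as the test of non-sleep PTSD symptoms.

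The cost is a wording change in those three sentences. The CAPS rates each symptom, so the item scores will already exist. No visit or test changes, and the N of 42 stands. The reported CAPS effect may be smaller than it would be on the full total.
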